7.3.5.2. Internal Consistency Reliability

Internal consistency reliability of each multi-item scale/domain score as identified by EFA results will be estimated using Cronbach's Alpha. Cronbach's Alpha, which ranges from 0 to 1, where "1" equals perfect reliability, is based on the average inter-item correlation and the number of items. Minimum values equal to or greater than 0.70 have been recommended for group level comparisons. Internal consistency will be tested for each domain of the CARES and *PROMIS Fatigue*, as well as for their total scores.

Internal consistency will also be assessed with the Cronbach Alpha statistics with Item Removal. Alpha will be estimated for each item and compared with the same statistic for the full set of

Document : /Users/[REDACTED]/Dropbox (Corvidia Tx)/Corvidia Tx Team Folder/Assets/COR-001/Clinical/RESCUE (COR-001-02)/Manuals & Plans/PRO
PAP/Corvidia_RESCUE_PAP_FinalV2.0_24APR2020.docx

Author: [REDACTED] Version No: V2.0

Version Date: 24APR2020

Template No.: [REDACTED] Reference: [REDACTED]

Effective Date: 01Dec2018

Copyright © 2018 [REDACTED] All rights reserved. The contents of this document are confidential and proprietary to [REDACTED] and its subsidiaries. Unauthorized use, disclosure or reproduction is strictly prohibited.

items. Items that do exhibit a strong drop in the Alpha value compared to the full set value should be selected for retention. Conversely items with alpha values for which there is small or no change from the full set value should be considered for removal.

7.3.6. CONSTRUCT VALIDITY

Validity refers to the evidence that the CARES and *PROMIS Fatigue* measure what they are designed to measure in the population for which it is intended. Construct validity is an experimental demonstration that the CARES and *PROMIS Fatigue* measures the core constructs of the symptoms of NDD-CKD patients at advanced stage. Three forms of construct validity will be examined: convergent, divergent, and known group validity.

7.3.6.1. Convergent and Divergent Validity

The Spearman Rank correlation coefficient will be used to evaluate convergent and divergent validity. Convergent validity refers to how well constructs that theoretically should be related to each other are observed to be related. Divergent validity can be viewed as the counterpart to convergent validity; it assumes that constructs theoretically unrelated to each other will be observed to be unrelated and will have low correlations.

Correlations between the CARES scores (items, TSS and any other scale/domain score as identified by EFA results) and *PROMIS Fatigue* scores (all scores identified in section 6.1.2) with the SF 36V2, EQ-5D-5L, and PGIS will be examined at Baseline. It is expected that there would be moderate to high correlations between domain and total scores of similar content across the assessments, and low correlations for non-overlapping domains.

PROMis Fatigue items 7 and 8 are keyed in the opposite direction of the remaining items and of those in the other instruments. Accordingly, those items should, regardless of the magnitude, show a negative correlation with other items and instruments.

Moderate Correlations

These are expected for CARES Tiredness (items 1, 2, 3, 4, 5) with the following domains:

- SF-36 v2: VT, GH, PF, RP, PCS, BP, MH , SF, RE, MCS
- EQ-5D-5L: Mobility, Self-care, Usual activities, Pain, Anxiety/Depression
- PGIS

and for CARES Items Gastrointestinal (6, 7) with the following domains:

- SF-36 v2: VT, GH, PF, RP, PCS, BP, MH , SF, RE, MCS
- EQ-5D-5L: Pain, Anxiety/Depression
- PGIS

Document : /Users/[REDACTED]/Dropbox (Corvidia Tx)/Corvidia Tx Team Folder/Assets/COR-001/Clinical/RESCUE (COR-001-02)/Manuals & Plans/PRO
PAP/Corvidia_RESCUE_PAP_FinalV2.0_24APR2020.docx

Author: [REDACTED] Version No: V2.0

Version Date: 24APR2020

Template No.: [REDACTED] Reference: [REDACTED]

Effective Date: 01Dec2018

Copyright © 2018 [REDACTED] All rights reserved. The contents of this document are confidential and proprietary to [REDACTED] and its subsidiaries. Unauthorized use, disclosure or reproduction is strictly prohibited.

and for *PROMIS Fatigue* Items 1 to 4 with:

- SF-36 v2: PF, RP, PCS, MH, RE, VT, MCS
- EQ-5D-5L: Mobility, Self-care, Usual activities, Anxiety/Depression

Low to Moderate Correlations

These are expected for CARES Items Mental Health (8, 9, 10) and Pain (11 12, 13) with the following domains:

- SF-36 v2: VT, GH, PF, RP, PCS, BP, MH , SF, RE, MCS
- EQ-5D-5L: Mobility, Self-care, Usual activities, Pain, Anxiety/Depression
- PGIS

and for *PROMIS Fatigue* Items 5 to 16 with:

- SF-36 v2: PF, RP, PCS, BP, MH , SF, RE, MCS
- EQ-5D-5L: Self-care, Usual activities, Anxiety/Depression

Low Correlations

These are expected for CARES Items Discomfort (14 to 19) with the following domains:

- EQ-5D-5L: Mobility, Self-care, Usual activities,

and for *PROMIS Fatigue* scores with:

- SF-36 v2: VT, GH, BP
- EQ-5D-5L: Pain
- PGIS

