2.4.1.1. CARES Corvidia

The CARES Corvidia ePRO - henceforth CARES - is a new PRO instrument under development (Appendix A). It consists of 19 symptom items, with a 24-hour recall, asking patients to report their worst level of that symptom in the past 24 hours on a numeric rating scale from 0 (no symptom) to 10 (symptom as bad as I can imagine).

The symptom items cover physiological (Short Breath, Swelling, Fatigue, Weakness, Light-headedness, Decreased Appetite, Nausea), psychological (Depression, Concentration, Forgetfulness), Pain (Bone / Joints, Nerves, Muscle Cramps) and sensorial (Hand numbness/tingling, Uncomfortable legs, Itching, Dry skin, Dry mouth, Cold) symptoms.

The instrument can be found in Appendix A.

2.4.1.2. Short Form *PROMIS Fatigue* 13a and selected items from *PROMIS Fatigue* Bank, *PROMIS Interest in Sexual Activity* Items

The *PROMIS Fatigue* 13a short form contains 13 items that assess symptoms and impacts of fatigue. The recall period is 7 days. Each item is rated on a five-point Likert scale ranging from 0 = "not at all" to 4 = "very much". Higher scores in these items indicate worst fatigue, except for items 7 ("I have energy") and 8 ("I am able to do my usual activities") where higher score indicates less fatigue.

In this study, three additional fatigue items were administered for further testing to account for exhaustion, being physically drained, and impact on alertness, concepts that resonated with patients during patient interviews but are not covered in the *PROMIS Fatigue* 13a short form. Such combination is from now on referred to as *PROMIS Fatigue*.

A number of scales and subscales can be derived from the *PROMIS Fatigue* set:

- The original *PROMIS Fatigue* 13a scale;
- The fatigue scale using the whole *PROMIS Fatigue* item set (*de novo* 16-item short form);
- Two subscales within the *PROMIS Fatigue* 13a scale, e.g.: 1) symptoms of fatigue and

Document : /Users/████████/Dropbox (Corvidia Tx)/Corvidia Tx Team Folder/Assets/COR-001/Clinical/RESCUE (COR-001-02)/Manuals & Plans/PRO
PAP/Corvidia_RESCUE_PAP_FinalV2.0_24APR2020.docx

Author: ██████████ Version No: V2.0

Version Date: 24APR2020

Template No.: ██████████ Reference: ██████████

Effective Date: 01Dec2018

Copyright © 2018 ██████████ All rights reserved. The contents of this document are confidential and proprietary to ██████████ and its subsidiaries. Unauthorized use, disclosure or reproduction is strictly prohibited.

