2.4.1.3. Short Form 36-item Health Survey, Version 2 (SF-36v2)

SF-36v2 is a self-report survey of functional health and well-being with 4 weeks recall period [QualityMetric 2011]. Responses to 35 of the 36 items are used to compute an 8-domain profile of functional health and well-being scores.

The remaining item, referred to as the 'Health Transition' item, asks patients to rate how their current state of health compared to their state of health 1 year ago, and is not used to calculate domain scores.

The 8-domain profile consists of the following scales: Physical Functioning (PF), Role Limitations due to Physical Health (RP), Bodily Pain (BP), General Health Perceptions (GH), Vitality (VT), Social Functioning (SF), Role Limitations due to Emotional Problems (RE), and Mental Health (MH).

Psychometrically-based physical and mental health component summary scores (PCS and MCS, respectively) are computed from subscale scores to give a broader metric of physical and mental health status. The instrument can be found in Appendix C.

2.4.1.4. 5-Level EuroQol in 5 dimensions (EQ-5D-5L)

The EuroQol EQ-5D-5L has been designed as an international, standardized, generic instrument for describing and valuing health-related quality of life, available in over 100 language versions.

The EQ-5D-5L self-report questionnaire consists of 5 items, one per domain, with a 5-point scale and one visual analogue scale (EQ VAS) to rate health state from worst (0) to best (100).

The EQ-5D-5L includes domains for each generic health status measure: Mobility, Self-care, Usual Activities, Pain/discomfort and Anxiety/depression. For each question, there are 5 levels of response, corresponding to increasing levels of impairment (no problems, slight, moderate, severe, and extreme problems or unable to perform activity) and coded 1 to 5.

Document : /Users/[REDACTED]/Dropbox (Corvidia Tx)/Corvidia Tx Team Folder/Assets/COR-001/Clinical/RESCUE (COR-001-02)/Manuals & Plans/PRO
PAP/Corvidia_RESCUE_PAP_FinalV2.0_24APR2020.docx

Author: [REDACTED] Version No: V2.0

Version Date: 24APR2020

Template No.: [REDACTED] Reference: [REDACTED]

Effective Date: 01Dec2018

Copyright © 2018 [REDACTED] All rights reserved. The contents of this document are confidential and proprietary to [REDACTED] and its subsidiaries. Unauthorized use, disclosure or reproduction is strictly prohibited.

A higher index indicates better quality of life. The instrument can be found in Appendix D.

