6.1.4. VARIABLES GENERATED FROM EQ-5D-5L

No derivation is required for the EQ-5D-5L. The scores for the 5 domains (Mobility, Self-care, Usual Activities, Pain/discomfort and Anxiety/depression) and EQ-5D VAS will be as reported. Missing data for individual items will not be imputed. For the psychometric analysis only the baseline scores will be used.

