Copyright © 2018 ██████████ All rights reserved. The contents of this document are confidential and proprietary to ██████████ and its subsidiaries. Unauthorized use, disclosure or reproduction is strictly prohibited.

Item Name	Question Text	Answer Text 1	Answer Text 2	Answer Text 3	Answer Text 4	Answer Text 5	Answer Text 6
SF36v2_VT1	How much of the time during the past 4 weeks did you feel full of life?	All of the time	Most of the time	Some of the time	A little of the time	None of the time	
SF36v2_MH1	How much of the time during the past 4 weeks have you been very nervous?	All of the time	Most of the time	Some of the time	A little of the time	None of the time	
SF36v2_MH2	How much of the time during the past 4 weeks have you felt so down in the dumps that nothing could cheer you up?	All of the time	Most of the time	Some of the time	A little of the time	None of the time	
SF36v2_MH3	How much of the time during the past 4 weeks have you felt calm and peaceful?	All of the time	Most of the time	Some of the time	A little of the time	None of the time	
SF36v2_VT2	How much of the time during the past 4 weeks did you have a lot of energy?	All of the time	Most of the time	Some of the time	A little of the time	None of the time	
SF36v2_MH4	How much of the time during the past 4 weeks have you felt downhearted and depressed?	All of the time	Most of the time	Some of the time	A little of the time	None of the time	
SF36v2_VT3	How much of the time during the past 4 weeks did you feel worn out?	All of the time	Most of the time	Some of the time	A little of the time	None of the time	
SF36v2_MH5	How much of the time during the past 4 weeks have you been happy?	All of the time	Most of the time	Some of the time	A little of the time	None of the time	
SF36v2_VT4	How much of the time during the past 4 weeks did you feel tired?	All of the time	Most of the time	Some of the time	A little of the time	None of the time	
SF36v2_SF2	During the past 4 weeks , how much of the time has your physical health or emotional problems interfered with your social activities (like visiting with friends, relatives, etc.)?	All of the time	Most of the time	Some of the time	A little of the time	None of the time	
	How TRUE or FALSE is each of the following statements for you?						
SF36v2_GH2	I seem to get sick a little easier than other people.	Definitely true	Mostly true	Don't know	Mostly false	Definitely false	

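### The PAP's blanket negative-correlation prediction for PROMIS Fatigue items 7 and 8 has the wrong sign for the SF-36 scores and EQ VAS

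*SAP*

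**What the plan says.** PAP v2.0 section 7.3.6.1 (Convergent and Divergent Validity) plans Spearman correlations of the CARES and PROMIS Fatigue measures "with the SF 36V2, EQ-5D-5L, and PGIS will be examined at Baseline". It then singles out two PROMIS items: "PROMis Fatigue items 7 and 8 are keyed in the opposite direction of the remaining items and of those in the other instruments". From that premise it draws a prediction of sign, with no exception for any instrument: "Accordingly, those items should, regardless of the magnitude, show a negative correlation with other items and instruments".

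The lists that follow grade the expected correlations as moderate, low to moderate, or low, without signs. PROMIS Fatigue Items 5 to 16, which include items 7 and 8, appear under low to moderate. They are set against eight SF-36 scores (PF, RP, PCS, BP, MH, SF, RE, MCS) and three EQ-5D-5L items (self-care, usual activities, anxiety/depression).

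The same PAP describes how the measures are keyed. Section 2.4.1.2 says items 7 and 8 are the two "where higher score indicates less fatigue". Section 2.4.1.4 describes the EQ-5D-5L as containing "one visual analogue scale (EQ VAS) to rate health state from worst (0) to best (100", and says its five domain items have response levels "corresponding to increasing levels of impairment". Section 6.1.4 keeps the VAS among the EQ-5D-5L scores: the domains "and EQ-5D VAS will be as reported".

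**The concern.** The sign prediction needs all the comparators to be keyed so that higher is worse. Some are not. EQ VAS and the SF-36 scores rise with better health, as items 7 and 8 do, so a patient with more energy and more preserved activity should score higher on all of them. One SF-36 Vitality question asks "did you have a lot of energy", which is close in content to PROMIS item 7.

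Convergent validity is judged by whether relations expected in advance are observed. If the expected sign is wrong, data from a sound item contradict the plan. The psychometric report must then either record an apparent failure or explain the expectation away after seeing the data. The same sentence stands in PAP v1.0 (section 7.3.2.1) and was not corrected when v2.0 was issued.

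**Working it through.** The plan gives no figure to reproduce. The check compares the keying of each measure, then counts.

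**Step 1. Direction of each measure**

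| Measure | Higher score means | Source | Expected sign with items 7 and 8, raw |
|---|---|---|---|
| PROMIS items 7 and 8 | less fatigue | PAP 2.4.1.2 | – |
| Other PROMIS Fatigue items | more fatigue | PAP 2.4.1.2 | negative |
| CARES | more symptoms | PAP 6.1.1 | negative |
| PGIS | more severe (none to severe) | PAP 2.4.1.5 | negative |
| EQ-5D-5L domain items | more impairment (1 to 5) | PAP 2.4.1.4 | negative |
| EQ VAS | better health (0 to 100) | PAP 2.4.1.4, 6.1.4 | positive |
| SF-36 domains, PCS, MCS | better functional health and well-being (implied) | PAP 2.4.1.3 | positive |

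**Step 2. Can any coding satisfy the sentence?** Let h be latent health, item = a·h + error, comparator = b·h + error. The correlation has the sign of a·b. In the table b is negative for some comparators and positive for others, so no single sign of a makes every product negative. Reverse-scoring the item flips every sign, so it repairs the SF-36 and EQ VAS predictions and breaks all the others.

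A one-factor simulation (200,000 draws, Spearman, equal loadings of 0.4, 0.6 and 0.8, which are assumed) illustrates this for a raw item 7:

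| Comparator | 0.4 | 0.6 | 0.8 |
|---|---|---|---|
| Another PROMIS item | −0.14 | −0.32 | −0.59 |
| CARES item | −0.15 | −0.33 | −0.60 |
| PGIS | −0.14 | −0.32 | −0.58 |
| EQ-5D-5L domain item | −0.14 | −0.32 | −0.58 |
| EQ VAS | +0.15 | +0.34 | +0.60 |
| SF-36 domain | +0.15 | +0.34 | +0.60 |

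Reverse-scored, the magnitudes are the same and every sign changes. The sizes depend on the assumed loadings; the signs do not.

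**Step 3. Count over the listed comparators for Items 5 to 16**

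- Per item: 8 SF-36 scores + 3 EQ-5D-5L items = 11 comparators.
- Wrong sign: the 8 SF-36 scores. Right sign: the 3 EQ-5D-5L items.
- Two items: 2 × 8 = 16 wrong of 2 × 11 = 22, or 73%.

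EQ VAS is outside this count because it is in none of the lists. The blanket sentence still covers it, as part of the EQ-5D-5L.

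**The case against.** The strongest reply is that nothing in the plan turns on this sign. That largely stands. Section 7.3.6.1 has no pass/fail criterion. Items become candidates for removal through floor or ceiling effects (7.3.1), item-to-item correlations within an instrument (7.3.2), item-total correlations (7.3.4) and alpha with item removal (7.3.5.2). None of these uses a correlation with the SF-36 or EQ VAS.

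Four stronger inferences are tempting, and the documents do not support them:

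- *Items 7 and 8 would be dropped or formally failed.* There is no rule that does this.
- *The efficacy scores would change.* The sentence passing sound scores to the efficacy analysis is in the factor-analysis section (7.3.3), and correlations with other PROs follow once scales have been proposed. The PRO SAP v2.0 fixes the total, symptom and impact scores from the 13-item set (5.5.2, 5.6), with item 7 in symptom and item 8 in impact (4.2.2).
- *A miscoded item would pass.* A reversed item would agree with the sentence for the SF-36 and EQ VAS only. It would violate it for the other PROMIS items, CARES, PGIS and the EQ-5D-5L domain items, and would show up in the item-to-item and item-total checks.
- *The error covers 20 of 32 predictions, or 22 of 34 with EQ VAS.* Ten SF-36 scores, five EQ-5D-5L items and PGIS is the list for CARES items 1 to 5, not for these PROMIS items.

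Two further replies carry some weight. The direction of the SF-36 scores is implied rather than stated, and scoring is left to the developer's manual (6.1.3), which is not reproduced. The Vitality question shows shared content, not score direction. Also, the main text plans the PROMIS correlations at score level; the item-level comparisons appear only in the lists.

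The sentence could also be read as being about raw questionnaire items. That does not rescue it. The SF-36 response options in Appendix C run both ways (limitation from most to least, pain from none to very severe), and the listed comparators are domain and summary scores.

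**Conclusion.** The point holds as an error in a pre-specified expectation. For EQ VAS the contradiction is explicit within the PAP. For the SF-36 it rests on reading functional health and well-being scores as higher-is-better, which the description implies. On that reading the stated sign is wrong for 8 of the 11 listed comparators per item, 16 of 22 in all, and no coding of the items meets the sentence in full.

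The consequence is limited. Followed literally, correctly behaving items would contradict most of the listed sign expectations, and the reported construct-validity conclusion for those two items would be misleading. The analysis is exploratory, no decision rule uses the sign, the fixed 13-item scores stand, and the hs-CRP endpoint is not touched.

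**What to change.** In PAP section 7.3.6.1, replace the blanket prediction with signs by instrument. For items 7 and 8 entered raw, expect positive correlations with the SF-36 domains, PCS, MCS and EQ VAS, and negative correlations with the other PROMIS Fatigue items, CARES, the EQ-5D-5L domain items and PGIS. Correct the premise so that it no longer says the two items are keyed opposite to all the other instruments. State that the items enter these correlations raw; if they are reverse-scored, all the signs flip. It would help to add one line in 6.1.3 giving the direction of the SF-36 scores.

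The cost is two or three sentences. No data collection, programming or planned analysis changes.

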The change in the CARES total score and EFA based scales from baseline (average of Day -7 to Day -1) to the Visit 7 (average of daily measurements from day 78 to day 84) will be used in the anchor-based analyses.

Document : /Users/[REDACTED]/Dropbox (Corvidia Tx)/Corvidia Tx Team Folder/Assets/COR-001/Clinical/RESCUE (COR-001-02)/Manuals & Plans/PRO
PAP/Corvidia_RESCUE_PAP_FinalV2.0_24APR2020.docx

Author: [REDACTED] Version No: V2.0

Version Date: 24APR2020

Template No.: [REDACTED] Reference: [REDACTED]

Effective Date: 01Dec2018

Copyright © 2018 [REDACTED] All rights reserved. The contents of this document are confidential and proprietary to [REDACTED] and its subsidiaries. Unauthorized use, disclosure or reproduction is strictly prohibited.

The same procedure will be applied to the *PROMIS Fatigue* total score and EFA-based scales using the matching 7-day recall measurement at baseline and Visit 7.

The adequacy of the anchors proposed above is explored with the Spearman correlations between the change from baseline to Visit 7 in CARES and *PROMIS Fatigue* total score and EFA-based scales. If the correlation coefficient >0.30, it will be emphasized in the interpretation of the results.

The following descriptive analyses will be conducted:

- Descriptive statistics for changes in the CARES total score and EFA-based scales from baseline (average of Day -7 to Day -1) to the Visit 7 (average of day 78 to 84). Descriptive statistics will be conducted for all categories as described in Table 2 Categories for change in PGIS and PGIC
- Descriptive statistics for changes in the *PROMIS Fatigue* total score and EFA-based scales from baseline to the Visit 7. Descriptive statistics will be conducted for all categories as described in Table 2 Categories for change in PGIS and PGIC
- Empirical cumulative distribution function plots (eCDF) and smooth Probability Density Functions (PDF) will be presented for each CARES and *PROMIS Fatigue* total score and EFA-based scales. These curves will be generated for all categories as described in Table 2.

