Furthermore, two descriptive tables will be generated to display change in the PRO scores from baseline at Visit 7 by baseline PGIS. This will be conducted separately for patients who achieved a 1-category and 2-category PGIS decrease at Visit 7 from baseline. Change scores will be categorized by percentiles: 10th, 25th, median, 75th, and 90th. Three baseline PGIS categories (i.e., mild, moderate, severe) will be used for the 1-category PGIS decrease analysis, while two categories for baseline PGIS (i.e., moderate, severe) will be used for the 2-category PGIS decrease analysis.

The various estimates from the different streams of evidence (distribution methods and anchor methods,) will be tabulated and will be examined for convergence in an effort to triangulate onto a single threshold value that represents meaningful within-patient worsening/improvement. However, if this is not possible, a range of thresholds will be considered.

The results of the anchor-based analyses (original, un-collapsed PGIS categories) will be considered primary when making decisions regarding the clinically meaningful worsening and clinically meaningful improvement thresholds and will be supplemented with eCDF and PDF curves. The primary anchor to establish the meaningfulness of deterioration or improvement in patient scores over time is PGIS. Specifically, our *a priori* definition of clinically meaningful deterioration threshold will be change from baseline of +1 points on the PGIS; and the *a priori* definition of clinically meaningful improvement threshold will be change from baseline -1 points on the PGIS. However, the results from other analyses will also be considered.

Document : /Users/[REDACTED]/Dropbox (Corvidia Tx)/Corvidia Tx Team Folder/Assets/COR-001/Clinical/RESCUE (COR-001-02)/Manuals & Plans/PRO
PAP/Corvidia_RESCUE_PAP_FinalV2.0_24APR2020.docx

Author: [REDACTED] Version No: V2.0

Version Date: 24APR2020

Template No.: [REDACTED] Reference: [REDACTED]

Effective Date: 01Dec2018

Copyright © 2018 [REDACTED] All rights reserved. The contents of this document are confidential and proprietary to [REDACTED] and its subsidiaries. Unauthorized use, disclosure or reproduction is strictly prohibited.

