7.3.2.4. Low Correlations

These are expected for *CARES* Items Discomfort (14 to 19) with the following domains:

- EQ-5D-5L: Mobility, Selfcare, Activity

and for *PROMIS Fatigue* Items 1 to 16 with:

- SF-36 v2: HT, GH, BP
- EQ-5D-5L: Pain
- PGIS

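### PAP v2.0 lists SF-36 Vitality as a low correlate of PROMIS Fatigue against its own text, and has no rule for when PGIS is too weak to lead the PROMIS threshold

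*SAP*

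**What the plan says.** All references are to PAP v2.0 unless another document is named.

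- **Expected low correlates of PROMIS Fatigue scores (7.3.6.1).** The list gives "SF-36 v2: VT, GH, BP", EQ-5D-5L Pain and PGIS. These correlations "with the SF 36V2, EQ-5D-5L, and PGIS will be examined at Baseline".
- **Expected moderate correlates of PROMIS Fatigue items 1 to 4 (same section).** The list gives "SF-36 v2: PF, RP, PCS, MH, RE, VT, MCS", so it includes Vitality.
- **General rule (same section).** "It is expected that there would be moderate to high correlations between domain and total scores of similar content across the assessments".
- **Known groups (7.3.6.2).** Baseline PGIS level is one of three grouping criteria across which CARES and PROMIS Fatigue scores are compared.
- **Thresholds (7.3.8 and 7.3.8.2).** Meaningful-change thresholds are derived for PROMIS Fatigue as well as CARES. "The primary anchor to establish the meaningfulness of deterioration or improvement in patient scores over time is PGIS", with one PGIS category up or down as the a priori definition.
- **Anchor adequacy (7.3.8.2).** Spearman correlations are computed on change from baseline to Visit 7. "If the correlation coefficient >0.30, it will be emphasized in the interpretation of the results". Nothing is said about a value that does not exceed 0.30.

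**The concern.** Two entries on one list do not fit the rest of the plan.

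Vitality is the SF-36 domain closest in content to a fatigue scale. Listing it as a weak correlate states the validity hypothesis the wrong way round, so a sound scale would contradict it.

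PGIS appears on the same list, yet it carries the main weight in deriving the PROMIS Fatigue thresholds. Those thresholds define improvement and deterioration in the PRO SAP v2.0 (section 4.2.2). They feed time to first and definitive deterioration (4.3 and 5.8) and the responder summaries (5.7). If PGIS turns out to be weakly related to change in PROMIS Fatigue, the plan leaves it primary by default. The cut-off used in those analyses could then say little about what patients regard as meaningful.

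**Working it through.** The plan states no figure on this point, so there is nothing to reproduce. The check is mainly a comparison of text, with two short calculations on labelled assumptions.

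**1. Item content.** The SF-36 Vitality items (Appendix C) ask about feeling full of life, having a lot of energy, being worn out ("did you feel worn out") and feeling tired. The PROMIS Fatigue items (PROMIS appendix) include feeling tired, having energy, and feeling listless or washed out. Two of the four Vitality items match almost directly, a third is close, and the fourth has no direct counterpart. The general rule in 7.3.6.1 therefore points to a moderate to high correlation.

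**2. Items against scores.** The moderate entry is for items and the low entry is for scores, so the two might be thought compatible. They are not. Section 7.3.6.1 takes the PROMIS scores from 6.1.2, and these include the five-item symptom score: items 1 to 4 plus the energy item. Suppose k items each correlate r with Vitality and m with one another. Their sum then correlates r × √(k / (1 + (k − 1)m)) with Vitality. Section 7.3.2.2 expects inter-item correlations above 0.50. With k = 4:

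- m = 0.50: √(4 / 2.5) = 1.26, so the sum correlates 1.26 r.
- m = 1: √(4 / 4) = 1, so the sum correlates r.

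Moving from items to a score keeps or raises the correlation. Moderate for the four items cannot sensibly become low for a score built mainly from them. This assumes equal correlations among the items.

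**3. Possible origin.** The superseded PAP v1.0 (section 7.3.2.4) had "SF-36 v2: HT, GH, BP" in this place, HT being the Health Transition item. HT also became VT in the CARES correlation lists.

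**4. PGIS roles.** For PROMIS Fatigue scores, PGIS is at once an expected weak correlate at baseline (7.3.6.1), a baseline criterion across which the scores should differ (7.3.6.2), and the primary anchor (7.3.8.2). For the CARES tiredness items, which include fatigue and weakness, 7.3.6.1 expects a moderate correlation with PGIS. No reason is given for expecting less of PROMIS Fatigue.

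**5. From baseline to change.** The PAP gives no number for low, so baseline correlations ρ of 0.1, 0.2 and 0.3 are assumed. Take rx and ry as the test-retest correlations of the two measures, with equal variances and the same ρ at both visits. Assume a lagged cross-correlation c = ρ√(rx·ry). Then:

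corr(change, change) = (ρ − c) / √((1 − rx)(1 − ry))

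For example, with ρ = 0.2, rx = 0.8 and ry = 0.6: c = 0.2 × √0.48 = 0.139, and (0.2 − 0.139) / √(0.2 × 0.4) = 0.217. Over the pairs (0.5, 0.5), (0.7, 0.5) and (0.8, 0.6):

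| Assumed baseline ρ | Implied change correlation |
|---|---|
| 0.1 | 0.10 to 0.11 |
| 0.2 | 0.20 to 0.22 |
| 0.3 | 0.30 to 0.33 |

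Under this structure a low baseline correlation carries over to a change correlation below or near 0.30. A different lagged cross-correlation would give a different answer, so this is an illustration and not a prediction.

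**6. Effect of a weak anchor.** If the relation is linear, the mean PRO change among patients whose anchor changes by a is:

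overall mean change + ρ × (SD of PRO change / SD of anchor change) × (a − mean anchor change)

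As ρ falls towards zero, the second term vanishes and every anchor group has the overall mean change. That gives the direction of the problem. Its size would need the two SDs and the correlation, and the documents give none of them.

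**The case against.** Four stronger readings are tempting, and the documents support none of them.

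- **That the plan itself predicts its primary anchor will be inadequate.** The low expectation is cross-sectional at baseline, has no number attached, and adequacy is checked on observed change scores. The plan does not forecast a weak change correlation.
- **That a good scale would be rejected over Vitality.** The lists in 7.3.6.1 are expectations with no pass or fail rule. Item removal is tied to floor and ceiling effects, item correlations and alpha. A high Vitality correlation would only disagree with a listed hypothesis.
- **That Vitality and PROMIS Fatigue ask the same questions.** Recall is 4 weeks against 7 days, the response options differ, and one Vitality item has no direct counterpart. The content overlaps clearly but is not identical.
- **That the Vitality entry is a documented replacement error.** The v1.0 list suggests this but does not prove it. HT also remains a derived score in 6.1.3.

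The plan also has partial safeguards for the threshold. PGIC is a second anchor, half-SD and one-SEM estimates are computed (7.3.8.1), and the eCDF curves are examined for separation between anchor groups. The estimates are triangulated, and a range is allowed if they do not converge. The derivation uses blinded data pooled over arms, so a poor threshold would be the same for all arms, and the PRO analyses are exploratory (PRO SAP v2.0, 5.1).

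These objections narrow the point without removing it. The Vitality contradiction stands on current text alone. For PGIS, none of the safeguards says when another source displaces the primary anchor.

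**Conclusion.** The Vitality entry is wrong as written. It contradicts another list and the general rule in the same section, as well as the item content, and this holds whatever its origin.

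The PGIS entry is an unreconciled tension, coupled with a real gap: 0.30 is the plan's only mark of anchor adequacy and nothing follows from missing it. The direction of harm is that a weak anchor moves the group-mean threshold towards the overall mean change, given a roughly linear relation. No size is claimed, because it would rest wholly on assumed SDs and correlations. Whether the gap matters in practice depends on the observed change correlation, which the plan will compute anyway.

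The consequences are confined to the psychometric report and the exploratory responder and time-to-deterioration analyses. The correction should be made because it is cheap and settles the anchor choice in advance.

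**What to change.** 1. In 7.3.6.1, move Vitality from the low list to the moderate-to-high convergent list for PROMIS Fatigue scores.
2. In the same list, reconcile the PGIS expectation with its known-groups and anchor roles: either remove PGIS from the low list or give the reason for expecting a low baseline correlation.
3. In 7.3.8.2, name both variables in the adequacy correlation and give it a consequence. PGIS is the primary anchor for a scale only if the absolute Spearman correlation between PGIS change and that scale's change to Visit 7 is at least 0.30. Otherwise PGIC leads, if it meets the same mark. If neither does, report a range of thresholds from the planned distribution-based and eCDF evidence, and carry them into the PRO SAP as sensitivity thresholds.

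Change in SF-36 Vitality might suggest itself as a further fallback anchor, but it is not proposed. It would be nearly circular for a fatigue scale, and 6.1.3 limits the SF-36 to baseline scores in the psychometric analysis.

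The cost is PAP wording and a few correlations on data already planned. The drawback is that CARES and PROMIS Fatigue thresholds may rest on different anchors, which the report would have to state.
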